The primary outcome will be the success rate of external cephalic version to cephalic presentation. Secondary outcomes will include: time from procedure to delivery, mode of delivery, patient discomfort, adverse events during procedure (ie.fetal bradycardia, emergent cesarean section, abruption), neonatal outcomes (ie. birthweight, Apgars, cord pH, NICU admission). The external cephalic version procedure may be terminated in any patient at any time regardless of this study in the event of persistent fetal heart rate abnormalities, maternal request, or any other adverse findings that the physician believes is an indication that the procedure must be terminated.

Protocol Was Already Approved by the Icahn School of Medicine at Mount Sinai (ISMMS) Institutional Review Board (IRB) Under a Different Principal Investigator No

Protocol Was Previously Submitted to an External(non-ISMMS) IRB No

4. Research Personnel

Name/Department	Role/Status	Contact	Access	Signature Authority	Phone	Email
[name] / Obstetrics/ Gynecology	PI /	Yes	SIGNAUTH			
[name] / Obstetrics/ Gynecology	Co-Investigator /		EDIT			
[name] / Obstetrics/ Gynecology	Co-Investigator /		EDIT			
[name] / Obstetrics/ Gynecology	Co-Investigator /		EDIT			
[name] / Obstetrics/ Gynecology	Co-Investigator /		EDIT			
[name] / Anesthesiology	Co-Investigator /		EDIT			
[name] / Anesthesiology	Co-Investigator /		EDIT			
[name] / Anesthesiology	Co-Investigator /		EDIT			

5. Sites

Site Name Mount Sinai West

Other External Site Name

Contact Details

Approved 0

Approval Document

Funded By Mount Sinai 1

Reviewed By Mount Sinai IRB

Other IRB

6. Subjects - Enrollment

Site Name	Mount Sinai Roosevelt
Subjects To Be Enrolled	
100	
Total	100

7. Subjects - Setting and Resources

Setting of Human Research Other

Specify Other Setting of Human Research

Labor and Delivery unit at Mount Sinai West hospital.

Total Number of Subjects Needed 100
To Complete Study

Feasibility of Meeting Recruitment Goals

From 2012-present we have attempted approximately 89-115 external cephalic versions a year. Each year we have been increasing in numbers, with 115 patients in 2015. These numbers only include patients who had an attempted ECV and does not include patients that were scheduled for ECV but the procedure was not performed for various circumstances. Given this information we believe that it will take approximately 1-2 years to recruit 100 patients.

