Facilities To Be Used for Conducting Research

We will be conducting our research on labor and delivery and the MFM fellow office located in Mount Sinai West Hospital, suite 10-C.

Multi-Center Study No

Community-Based Participant Research Study No

PI must attest to the following. * Process is adequately described to ensure that all persons assisting with the trial are adequately informed about the protocol, the investigational product(s), and their trial-related duties and functions.

8. Subjects - Populations

Inclusion Criteria

Singleton pregnancies of at least 37 weeks gestation in nonvertex presentation with no contraindication for a vaginal delivery. Membranes must be intact with a minimum of a 2x2 pocket and Category 1 non-stress test.

Exclusion Criteria

All patients with a contraindication for a vaginal delivery will be excluded from the study, as well as those patients with gross fetal anomalies or uterine malformations. Patients with contraindications to neuraxial anesthesia or allergies to any of the study medications will also be excluded.

Enrollment Restrictions Based Yes
Upon Gender, Pregnancy,
Childbearing Potential, or Race

Justify Restriction(s)

Patient must be pregnant in order to enroll because this is a study involving fetal versions.

Age Range(s) 18 to 64 Years

Targeted Population(s) Adults - Patients , Pregnant Women

Other Aspects that Could Increase Subjects Vulnerability

There are no further aspects that could increase the subjects vulnerability.

Safeguards to protect Subjects rights and welfare

In order to protect the subjects rights we will be consenting the patients and allowing them to decide if they would like to participate. Patients will be assured that their decision to participate in the study is completely optional and that their care will not be altered in the event that they do not wish to participate. Patients will be given time to decide if they would like to participate and all questions will be answered.

9. Subjects - Participation

Duration of an Individual Subjects Participation in the Study

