The individual subject will be participating in the study for approximately 1-8 hours depending on how long the procedure takes. We will then follow-up their delivery information using labor and deliveries' EMR (Peribirth). The patient will not be contacted at this time. Once delivered they will no longer be part of the study. Delivery usually occurs within 5 weeks of the procedure given that the procedure is only done at 37 weeks or higher.

Duration Anticipated to Enroll All Study Subjects

We will be enrolling study subjects for 2 years.

Estimated Date for the Investigators to Complete This Study Within two years

Procedures for Subjects to Request Withdrawal

Patients can withdraw at anytime and will be aware of that option. We will be conducting an intention-to-treat analysis. If the patient decides to withdraw we will then ask the patient if we can still collect their demographic and delivery data. If they allow this, then they will be included in the analysis and this will be stated in our results once the study is written. No identifiers will be included in the results. If they would like to withdraw completely we will not collect any further data and we will not include them in our analysis.

Procedures for Investigator to Withdraw Subjects

There is no circumstance that the patient will be withdrawn without their consent. There is no anticipated reason that a patient would need to be terminated from the study. If there is any concern that there is risk to the fetus during the procedure, the procedure will be terminated and the patient will still be included in the study. This will then be discussed and explained in our study results.

Participants Will Be Recruited Yes
Recruitment Method(s) Clinical Practice

How Participants Will Be Identified

Each day external cephalic versions are scheduled on labor and delivery. When a patient is noted to be scheduled for a version, once they are admitted and there is no contraindication noted for the participation in the study (for example, they come for a version but are found to be in the cephalic presentation that day) they will be asked if they are willing to participate in a study. If the patient agrees, a member of the research team will approach the patient and discuss the study with the patient.

Who Will Initially Approach Potential Participants Study Personnel

How Research Will Be Introduced to Participants

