Accessing Data Yes

Receipt or Transmission of Data Yes

Holding Code That Can Be Linked to Identity of Participants No

Research Personnel Responsible for: [name]

Accessing Data Yes

Receipt or Transmission of Data Yes

Holding Code That Can Be Linked to Identity of Participants No

Research Personnel Responsible for: [name]

Accessing Data Yes

Receipt or Transmission of Data Yes

Holding Code That Can Be Linked to Identity of Participants No

Research Personnel Responsible for: [name]

Accessing Data Yes

Receipt or Transmission of Data Yes

Holding Code That Can Be Linked to Identity of Participants No

Research Personnel Responsible for: [name]

Accessing Data Yes

Receipt or Transmission of Data Yes

Holding Code That Can Be Linked to Identity of Participants No

Research Personnel Responsible for: [name]

Accessing Data Yes

Receipt or Transmission of Data Yes

Holding Code That Can Be Linked to Identity of Participants No

Research Personnel Responsible for: [name]

Accessing Data	Yes
Receipt or Transmission of Data	Yes
Holding Code That Can Be Linked to Identity of Participants	No

Duration Data Will Be Stored

Data will be stored until the data is analyzed, within 1 year from study completion.

Steps That Will Be Taken to Secure the Data During Storage, Use, and Transmission

The study investigators will collect medical information about the subject over the course of the study. Study data will be entered into a de-identified research database, using a unique code numbering system. A code number linked to subject identity will be used instead of names. The code number will not be derived from any patient identifiers, such as patient name or medical record number. The record linking the subjects' name with their assigned codes will be kept on the computer in a separate secure folder. All files are password protected on a secure server.

Data Analysis Plan Including Any Statistical Procedures

Continuous variables will be analyzed using two tailed T-test and categorical variables will be analyzed using Pearson Chi Square test. Logistic regression will be used to adjust for confounders. A p-value <0.05 will be considered significant.

22. Data - Safety Monitoring

More Than the Minimum Data Safety Monitoring Will Be Done No

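### Time from procedure to delivery is compared by an unadjusted t-test, which gives up precision that gestational age at version, known for every patient, could supply at no cost

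*Combined protocol and SAP*

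**What the plan says.** Section 3 (Primary and Secondary Study Endpoints) puts the interval first among the secondary outcomes: "Secondary outcomes will include: time from procedure to delivery, mode of delivery, patient discomfort".

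The Data Analysis Plan in section 21 is four short statements. "Continuous variables will be analyzed using two tailed T-test"; categorical variables get Pearson chi-square; "Logistic regression will be used to adjust for confounders"; and "A p-value <0.05 will be considered significant". No covariates are named, and no linear model or time-to-event model is mentioned.

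Section 8 (Inclusion Criteria) admits "Singleton pregnancies of at least 37 weeks gestation in nonvertex presentation", with no upper limit. Section 9 (Duration of an Individual Subjects Participation) makes the link to the interval itself: "Delivery usually occurs within 5 weeks of the procedure given that the procedure is only done at 37 weeks or higher".

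On when versions are actually done, the opening summary has breech noted at 37 weeks, and section 3 (Background) puts the version at about 37 weeks. Section 19, which lists the data to be recorded, does not name gestational age at version. The study form listed in section 15 is not shown.

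**The concern.** The interval is gestational age at delivery minus gestational age at version, so the second quantity is an arithmetic component of the outcome. A woman verted at 39 weeks has about two weeks less available than one verted at 37. That variation has nothing to do with treatment, yet a comparison of raw means leaves it in the error term.

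The plan shows an intention to adjust, but the method it names is for binary outcomes. As written, this outcome is therefore unadjusted.

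Two things are at stake: a wider confidence interval than necessary, and an estimate that carries most of whatever difference in gestational age at version arises by chance between the arms.

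**Working it through.** **Stated figure.** There is none to reproduce. The documents give no SD, effect size or power for this outcome, and the total of 100 is supported only by recruitment feasibility.

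**Inputs from the documents.** N = 100 (sections 6 and 7); alpha 0.05, two-tailed (section 21); versions at about 37 weeks (opening summary and section 3) or later (sections 8 and 9).

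**Assumptions.**
- Allocation is 1:1, 50 per arm; the ratio is not stated.
- Delivery age is Normal with mean 39.3 weeks and SD 0.8, 1.0 or 1.3 weeks, restricted to after the version and before 42 weeks.
- Gestational age at version is uniform over one of four ranges.

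**Formulas.** Let ρ be the correlation between gestational age at version and the interval.
- Share of variance explained = ρ².
- Equivalent unadjusted sample = 100 / (1 − ρ²).
- 95% CI half-width in units of the outcome's SD = 1.96 × √(2/50) × √(1 − ρ²), which is 0.392 without adjustment.

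**Simulated results.** Each cell runs from delivery SD 1.3 to delivery SD 0.8.

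| Versions spread over | ρ² | Equivalent N | Slope of interval on gestational age |
|---|---|---|---|
| 37.0-37.5 weeks | 0.01 to 0.03 | 101 to 103 | −0.80 to −0.96 |
| 37-38 weeks | 0.04 to 0.11 | 104 to 112 | −0.74 to −0.92 |
| 37-39 weeks | 0.13 to 0.28 | 114 to 139 | −0.64 to −0.79 |
| 37-40 weeks | 0.20 to 0.37 | 125 to 159 | −0.56 to −0.68 |

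The half-width falls from 0.392 SD to 0.392 × √0.99 = 0.390 SD at the low end and to 0.392 × √0.63 = 0.311 SD at the high end.

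**Cost of the covariate.** Estimating one slope inflates the variance by about 1/(N − 4) = 1/96, or 1%. At the bottom of the narrowest range the net gain is therefore about nil; elsewhere it is positive.

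**Chance imbalance.** The 95% chance range for the between-arm difference in mean gestational age at version is ±1.96 × SD × √(2/50), shown here for delivery SD 1.0.
- Versions over 37.0-37.5 weeks (SD 0.144 weeks): ±0.056 weeks, or ±0.40 days. Multiplied by the slope of 0.90, about ±0.4 days reaches the estimate.
- Versions over 37-40 weeks (SD 0.79 weeks): ±0.31 weeks, or ±2.2 days. Multiplied by the slope of 0.62, about ±1.3 days reaches the estimate.

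This is not additional to the t-test's confidence interval. It is the part of that interval which adjustment removes.

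**The case against.** The strongest case against is that nothing here is an error. Randomization makes the t-test unbiased, and its type I error already allows for chance imbalance in gestational age. The outcome is secondary, and the plan attaches no power or decision to it. That stands, and it limits the point to efficiency.

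The second objection is that the protocol describes versions at about 37 weeks. If they cluster there, the gain is 1-3% before the cost of the covariate, which is negligible. That also stands as a possibility. Eligibility has no upper limit, however, and section 9 speaks of 37 weeks or higher, so the documents do not settle the spread.

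Three stronger readings are tempting, and the documents do not support them.

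- *A chance imbalance passes into the estimate one-for-one.* This needs a slope of exactly −1. Because delivery must follow version, women verted later also deliver later on average, and the simulated slopes are about −0.56 to −0.96.
- *The gain can be read from the two SDs as if the ages were independent.* With SDs of 0.6 weeks at version and 1.0 at delivery, that formula gives 0.36 / (0.36 + 1.00) = 26%; with 0.8 and 0.8 it gives 50%, a doubling of the effective sample. Independence fails for the same reason, and the simulation stops at 37%.
- *Gestational age at version is not collected.* Section 19 does not name it, but its demographic list is illustrative, ultrasound findings are recorded, dates of service are kept (section 12), and the form is not shown. It may already be there.

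**Conclusion.** The point holds as a free improvement in precision on one secondary outcome. The stated test ignores a baseline value that must be known before the procedure and that the protocol itself ties to the interval. The one adjustment method the plan names cannot be used for it.

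The size runs from practically nothing to an effective sample of about 159 instead of 100. It depends mainly on how widely gestational age at version is spread, which the documents do not give. It also rests on the assumed 1:1 allocation and delivery-age distribution. A reader might infer that the planned comparison is biased or invalid; under randomization it is neither. The primary outcome, success of the version, is not touched.

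**What to change.** 1. **Data (section 19 and the study form).** Confirm that gestational age at version is recorded in days for every patient, and add the field if it is not. The value is already established at screening. This is best settled before data collection ends, because section 12 has the linked code and data deleted after analysis.
2. **Analysis (section 21).** Add one line: time from procedure to delivery will be analysed by linear regression on randomized arm and gestational age at version in days, reporting the adjusted difference with a 95% CI. Keep the t-test as a supportive analysis. Fix the covariate before outcomes are seen, so that adjustment cannot be chosen on the result.

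The cost is at most one data field, one sentence and one degree of freedom. It needs no extra patients, visits or procedures.
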